17.2 Sub-group & interim analysis

Analysis will be split by the organ system of the infection (i.e. lower urinary tract, lower respiratory, intra-abdominal, bacteraemia, skin and soft tissue etc).

Stratified analyses will be undertaken at different levels of NEWS2 scoring ≤ 4 , 5-6 and ≥ 7 .

Stratified analysis will also be undertaken by COVID status.

For the interim analysis due to the group-sequential design a separate interim SAP will be created. The interim analysis will be stratified by risk category (Figure 1).

18 Health inequalities and health economics

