The following amendments and/or administrative changes have been made to this protocol since the implementation of the first approved version.

Amendment No.	Protocol version no.	Date issued	Summary of changes made since previous version
Substantial (Amendment 4)	2.0		
 1. Change in Site PI and Co-Investigators 2. Changes in CTR team 3. Added COVID related background. 4. Change to risk stratification for high NEWS (≥ 7) and low PCT (< 0.05) to moderate risk. 5. Consent process altered in section 9.3 6. Added planned stratification of all outcomes by COVID-19 diagnosis 7. It should read "low PCT (< 0.5)" rather than "low PCT (< 0.05)" 8. Added Covid to the list of variables to be collected. 9. Added COVID diagnosis to table 1. 10. Added witness consent to Qualitative interviews. 11. Subgroup and interim analysis updated.
Non-substantial (Amendment 18)	2.1		
 1. Updated final decisions on primary effectiveness (section 5.3). Decreased mortality with same or

Substantial (Amendment 23)
	
3.0
		
equivalent antibiotic initiation changed from 'unclear effect' to 'Effective'.
 
 1. Inserted website information for randomisation, 2. Updated research administrator at CTR. 3. Updated qualitative researchers at CTR. 4. Updated planned number of sites (Section 2) 5. Updated planned trial period (Section 2). 6. Number of sites updated in setting information (Section 6.2). 7. Updated information on the trial intervention to include PathFast BRAHMS PCT reader (section 10)
---	------------	--	--

2 Synopsis

Short title	PROcalcitonin and NEWS2 evaluation for T imely identification of sepsis and O ptimal use of antibiotics in the Emergency Department
Acronym	PRONTO
Internal ref. no.	UoL001520
Development phase	Phase III
Funder and ref.	NIHR HTA (ref 17/136/13)
Trial design	Prospective, individually randomised, open label, two arm, group sequential RCT
Trial participants	Adults and adolescents ≥ 16 years presenting to emergency care departments with suspected sepsis.
Planned sample size	7676
Planned number of sites	Maximum of 20 sites
Inclusion criteria	Patients ≥ 16 years presenting to the ED with suspected sepsis

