5.4 Secondary outcomes measure(s)

Time until initiation of IV antibiotic therapy

Late IV antibiotic initiation – antibiotics commenced after 3 hours

Number of days on IV antibiotics (during admission and total over the first 28 days).

Number of days on any antibiotic (during admission and total over the first 28 days).

Number of days on broad spectrum antibiotics (IV and oral), defined by number of days on an Access group of antibiotics as defined by WHO [AWaRe Classification Database](#) (during admission and total over the first 28 days).

ICU admission – at any point during admission

Length of ICU stay

Length of hospital stay

Adverse antibiotic outcomes

Readmission to hospital within 90 days

Mortality within 90 days (and time until death)

Health utility (EQ-5D/5L) at 28 and 90 days

Health resource usage

Feasibility of implementing PCT testing alongside NEWS2 scoring in EDs

Acceptability of implementing PCT testing alongside NEWS2 scoring in EDs, to patients, carers and clinicians

Planned stratification of all outcomes by COVID-19 diagnosis

6 Trial design and setting

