This will be used in combination with NEWS2 assessment of adult patients with suspected sepsis in ED, using a guidance-only algorithm for clinicians (see flow chart). It is important to note that clinicians have oversight at all times as to whether to adhere to the algorithm. As currently mandated in NICE clinical guidelines and quality standard QS161, urgent senior review within an hour will take place where any health care provider identifies at least one risk factor indicating high risk of severe illness or death regardless of aetiology. In the intervention arm a NEWS2 score of 5 or 6, combined with a PCT score of <0.5 indicates a low risk of bacterial sepsis, but an urgent senior review is mandated on the basis of the elevated NEWS2 score in keeping with standard QS161. For participants who are identified as medium risk, urgent senior review will occur. Antibiotics will be delivered according to clinical assessment. For participants in the high risk categories (Figure 1, red boxes), antibiotics will be given within the hour along with blood tests and IV fluids given as per standard care.

The PCT result is a decision aid and not to be used as a definitive management decision tool. Trained HCPs will perform the test in the ED, without the need to send the PCT sample to the laboratory. A rapid result, especially if it indicates a low or medium risk, may provide reassurance to patients and families, and reduce anxiety.

[figure not shown]
Full administrator level training will be provided by Thermofisher or AB Scientific at each site with all users following the appropriate Standard Operating Procedure for QC measurement and routine work flow processes (see example of BRAHMS PCT Direct in Figure 3). For the BRAHMS PCT Direct, Research Nurses or appropriately delegated HCPs will have a unique 4-

digit log in code for the reader. Adults in the control arm will not have the PCT test performed and will simply have NEWS2 assessment for suspected sepsis as per standard care.

Thermo Scientific B·R·A·H·M·S direct Reader

Routine workflow

1/3

thermo scientific

Figure 3. Routine work flow for BRAHMS PCT-Direct Reader.

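### The interim analysis is stratified by a risk category that uses PCT, which only the intervention arm has, so comparisons within or adjusted for these strata are not randomised comparisons

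*Protocol*

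**What the plan says.** Section 17.2 plans a separate interim SAP and then fixes one feature of it: "The interim analysis will be stratified by risk category (Figure 1"). The same section lists stratification by NEWS2 band (≤4, 5-6, ≥7) as a separate item.

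Section 10 describes the category. In the intervention arm "a NEWS2 score of 5 or 6, combined with a PCT score of <0.5 indicates a low risk of bacterial sepsis", and the highest categories are identified with the same figure: "For participants in the high risk categories (Figure 1, red boxes), antibiotics will be given within the hour". The amendment history points the same way, with an entry that begins "Change to risk stratification for high NEWS (≥ 7) and low PCT" and moves that cell to moderate risk. I use that entry as support only. For controls, section 10 says "Adults in the control arm will not have the PCT test performed".

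NEWS2 is known in both arms before allocation. Section 9.4.2 uses it as a minimisation factor and section 17.1 adjusts the primary models for it.

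**The concern.** A stratifier protects a randomised comparison only if it is fixed before allocation, or at least by the same rule in both arms. This one is neither. A control patient with NEWS2 of 5 or 6 and an unmeasured low PCT stays in the class that NEWS2 alone gives. An identical patient in the PCT arm is classed as low risk. The low, moderate and high strata then hold different kinds of patient in the two arms, and their event rates differ for that reason alone.

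The interim look informs an IDMC recommendation to stop for effectiveness or futility. Stratified tables, or a stratum-adjusted estimate, could show harm or benefit that is only reclassification.

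**Working it through.** **1. Scale from the protocol.** Section 16.2 assumes 15% mortality, a 2.5-point margin, one-sided 5% and 90% power. Per arm, n = (1.645 + 1.282)² × 2 × 0.15 × 0.85 / 0.025² ≈ 3495, or 6990 in total against the stated 7002, so the figure reproduces. At the interim about 7676 × 0.95 / 2 ≈ 3646 patients have data, 1823 per arm. The SE of the unstratified mortality difference is √(2 × 0.15 × 0.85 / 1823) ≈ 0.0118, about 1.2 points. The protocol gives no figure for the stratified analysis.

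**2. Assumed inputs (not in the protocol).** For NEWS2 ≤4 / 5-6 / ≥7:
- shares 35 / 40 / 25%
- mortality 7 / 13 / 29.4%, giving 0.35 × 7 + 0.40 × 13 + 0.25 × 29.4 = 15.0% overall
- IV antibiotic initiation 80 / 93 / 99%
- P(PCT <0.5) either 60 / 50 / 35% or 80 / 70 / 50%
- mortality odds ratio for PCT ≥0.5 against <0.5 within a band: 1, 2 or 3

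There is no treatment effect. Controls are classed low / moderate / high by NEWS2 band.

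**3. Mappings for the PCT arm.** Only two cells can be read from the text: NEWS2 5-6 with low PCT (low risk, section 10) and NEWS2 ≥7 with low PCT (moderate, amendment history). The rest is assumed.
- A: low PCT moves those two cells down; high PCT leaves the NEWS2 band unchanged.
- B: as A, but high PCT also moves NEWS2 ≤4 to moderate and 5-6 to high.

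**4. Formulas.** The stratum rate in an arm is Σ(share × rate) / Σ share over the cells assigned to it. The pooled difference uses Mantel-Haenszel weights w = s_I × s_C / (s_I + s_C), where s_I and s_C are the stratum's shares of the intervention and control arms.

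**5. Worked case: mapping A, PCT 60/50/35%, odds ratio 1.**
- Low: (0.35 × 7 + 0.20 × 13) / 0.55 = 9.2% against 7.0%, difference +2.2; w = 0.214
- Moderate: (0.20 × 13 + 0.0875 × 29.4) / 0.2875 = 18.0% against 13.0%, difference +5.0; w = 0.167
- High: 29.4% in both, difference 0; w = 0.098
- Pooled: (0.214 × 2.18 + 0.167 × 4.99) / 0.480 = +2.7 points

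PCT has no prognostic value here. The shift arises because NEWS2 bands are mixed in one arm only.

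**6. Range over the inputs in step 2** (intervention minus control, percentage points, true difference zero):

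| Mapping | Low | Moderate | High | Pooled mortality | Pooled antibiotic initiation |
|---|---|---|---|---|---|
| A | +0.1 to +2.7 | +5.0 to +8.4 | 0 to +11.0 | +2.7 to +4.9 | +2.7 to +3.8 |
| B | -1.4 to +3.0 | +0.2 to +8.4 | -9.0 to +2.3 | -1.3 to +1.7 | -0.2 to +2.0 |
| NEWS2 band in both arms | 0 | 0 | 0 | 0 | 0 |

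Under B with more low results (P(PCT <0.5) 90 / 80 / 60%, odds ratio 1 to 3) the pooled mortality shift is +3.2 to +3.6.

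**7. Only the cell that section 10 states.** If only NEWS2 5-6 with low PCT is moved, using the inputs of step 5, the low stratum differs by +2.2 and the others by 0. The weights are 0.214, 0.133 and 0.125, so the pooled shift is 0.214 × 2.18 / 0.472 = +1.0 point. The bias does not depend on the amendment-history entry.

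**The case against.** **The stopping rule.** A reader might infer that the IDMC would decide from biased strata. The protocol does not say so. Sections 16.2 and 17.1 state the criteria on the co-primary outcomes, with no stratum condition. Section 17.2 does not say whether stratified means separate tables, a covariate or a pooled test. The unstratified intention-to-treat comparison is unbiased, and the final analysis adjusts for baseline NEWS2. All of this stands and limits the consequence.

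**The unseen figure.** Figure 1 is not reproduced. Section 14.1 speaks of risk at presentation for interviewees from both arms, so a baseline meaning is conceivable. Section 10, however, ties the Figure 1 boxes to categories that use PCT, and section 17.2 lists the NEWS2 bands separately, so the PCT reading is the natural one. Classing controls with NEWS2 5-6 as moderate is also an assumption.

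**Direction.** A reader might infer that the PCT arm must look worse in every stratum. It need not: under mapping B the sign can change. Only the non-comparability is established.

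**The interim SAP.** It could redefine the category, but the protocol itself names the stratifier, so this is a rule fixed badly rather than a detail left open.

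**Other splits.** A reader might extend the point to organ system ("Analysis will be split by the organ system of the infection") and COVID ("Planned stratification of all outcomes by COVID-19 diagnosis"). The documents do not support that. PCT does not define those groups. Table 1 collects the COVID item at day 28 but records a date, from which status at presentation could be derived. No time is stated for classifying infection source. Bias there would need work-up or labelling to differ by arm. At most, splits that use diagnoses made after randomisation should be treated as exploratory.

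**Conclusion.** The point holds for the interim stratifier. As written, section 17.2 uses a category formed after randomisation and by a different rule in each arm, so comparisons within or adjusted for it are not randomised comparisons. With no treatment effect, the illustrations give pooled mortality shifts from -1.3 to +4.9 points, against a 2.5-point margin and an interim SE of about 1.2 points. Antibiotic initiation shifts as well. These sizes rest on assumed NEWS2 shares, event rates, PCT distributions and most of the Figure 1 mapping. They show that the bias can matter; they do not predict it. The unstratified interim comparison and the final primary analysis are not affected, and no stated stopping boundary is shown to be wrong. The risk is that stratified interim results mislead the IDMC.

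**What to change.** Replace the sentence in section 17.2 with: *In both arms, interim results will be stratified by the NEWS2 band recorded before randomisation (≤4, 5-6, ≥7).* Add: *PCT-based risk categories will be reported descriptively, within the PCT arm only.* Carry the same wording into the interim SAP.

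The cost is a wording change in the protocol and the interim SAP. NEWS2 is already collected in both arms before allocation and the bands are already defined in section 17.2, so no new data are needed and no clinical rule is touched.

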18.1 Health Inequalities

The outcomes in the trial will be assessed from a health equity perspective [40]. We will collect data *a priori* to allow us to understand the contribution of social inequality to the study findings. Reducing health inequalities is a public health priority in the UK. Infectious diseases cause 7% of deaths and cost 30 billion pounds annually in the United Kingdom and are more common in disadvantaged populations. People living in more disadvantaged circumstances are more likely to have established ill health, be exposed to risk factors for infectious diseases, such as poor housing quality and nutritional status, and also experience worse outcomes with disability and mortality. A secondary aim of this study is therefore to examine the trial dataset from a health equity perspective. The study will be undertaken in sites which will include participants from a wide range of socio-economic backgrounds, and we will collect data on individual and area level measure of SES [41]. We will conduct analyses to examine how the effects of the PCT-guided evaluation under investigation on clinical and healthcare outcomes are moderated by SES in order to assess the intervention impact on health inequalities. These analyses will be tested as part of the pilot.

In addition, we will assess the association of SES with outcomes across the care pathway for people with sepsis. For example, we will explore the extent to which key risk factors for poor outcomes, such as co-morbid conditions, disease severity at presentation, and health behaviours may mediate any association between SES and sepsis mortality. We will also explore any variations in clinical care (for example duration of hospital stay, cost of care, rates of readmission, patterns of antimicrobial use, adverse events related to antimicrobials) on the basis of SES. This study will be the first in recent times to assess social inequalities in the healthcare consequences and outcomes of sepsis in a large population in the UK and should help design better policies and pathways to reduce health inequalities for people with sepsis in the UK.

18.2 Health Economics

Economic analyses of the project have been planned based on expected primary and secondary outcomes of health intervention. As per the primary research question of the project, we expect that in ED patients managed as suspected sepsis, the addition of PCT to the NEWS2 scoring measurement may lead to a reduction in antibiotic initiation with at least no increase in 28-day mortality compared to the NEWS2 scoring alone. The secondary research question considers a broader aspect of economic evaluation that includes the societal perspective including the preferences of patients and family members. So, it examines if the proposed intervention would be cost-effective from the societal perspective (including household consequences).

In economic analyses, we shall apply NHS and societal perspective to address the decision making in the health system and on the society respectively. They will follow the intention-to-treat of the primary clinical effectiveness and safety analyses. Missing economic data will be imputed in a standard manner. The costs borne by NHS and the patients will thus be considered in estimations wherever applicable.

- 1) Cost of illness per patient from sepsis in intervention arm (IA: PCT + NEWS2) and standard care arm (SCA: NEWS2 alone), from the NHS and patient household perspectives.
- 2) Cost-saved per unit investment into proposed IA due to avoided antibiotic prescription, reduction of hospitalizations, and other cost-savings
- 3) Cost-effectiveness analysis of proposed intervention (PCT + NEWS2) in comparison to standard care per life year saved and £ per QALY gained
- 4) Cost-benefit analysis of proposed intervention (PCT + NEWS2)

18.2.1 Methods

1) Cost of illness

The cost of illness (COI) will be conducted using NHS perspective and patient's perspectives. Together these will constitute the societal perspective. It implies that data will be collected from two sources, i.e. the hospital and patients. Total costs of illness of sepsis care per patient from the ED to hospitalization will be estimated for the treatment of sepsis by multiplying the total incidences of sepsis with the unit cost of caring for a patient throughout an episode up to 28 days after discharge from hospital. In addition, the total cost of screening will be included, again both from health service and household perspective. Considering the need of care, 30 patients of each type (general ward and ICU), of 10 hospitals will be included to calculate the mean costs of illness, which will sum up a total of $30 \times 2 \times 10 = 600$ patients. Direct medical and non-medical as well as indirect costs (income loss) will be captured using a Standardbred questionnaire for patients and departmental- and patient-level costs from hospitals. By multiplying mean cost with incidence rates, the total costs will be estimated.

2) Cost saved per GBP invested in the proposed PCT intervention due to potentially avoided antibiotic prescription, avoided admissions, and other decreased resource use.

Here, the net cost of intervention is to be compared with the cost saved on avoidable antibiotics to estimate the money saved per GBP invested in the intervention arm. The outcome data of the intervention in terms of antibiotic avoided will be collected from a comparison of the two arms. The difference in antibiotic prescribing (number of patients and dosages) for patients between IA and SCA will be recorded from the ED and hospital prescription records. The unit price of antibiotic per dose will be multiplied by the doses avoided. Together with the savings due to reduced hospital admissions this will capture the total costs of antibiotic avoided due to the proposed intervention. The costs of intervention will be captured by identifying and quantifying the inputs used for patients in IA and SCA, valuing the inputs into economic costs with necessary (if applicable) adjustments for time preferences [42]. Such costs of intervention from the existing UK study by Hex et al. [43] might be used if not available in the reporting hospitals. Incremental costs between IA and SCA will constitute the investment on the proposed intervention for comparing with costs saved due

to reduced antibiotic use. It should be noted here that this intervention cost will be used in the cost-effectiveness analysis (CEA) (point 3 below) and cost-benefit analysis (CBA) (point 4 below) for comparing with intervention outcomes.

3) Cost-effectiveness analysis of proposed intervention (PCT + NEWS2) in comparison with standard care.

i) Cost-effectiveness approach

Our CEA will be influenced by the assumption that the outcome on 28 day mortality of IA and SCA is non-inferior (no significant difference). It means that the CEA will in the first instance take the nature of a cost-consequence (minimization) analysis and only the costs of interventions (IA and SCA) need to be compared to find the cost-effective alternative [42, 44]. Here, sepsis care with lower costs (i.e. intervention costs), defined by cost per screened patient and cost per sepsis patient treated will be considered as the more cost-effective alternative.

ii) Cost-utility analysis

Cost-Utility Analysis (CUA) of non-inferiority trials has been conducted elsewhere [45]. For decision making from the analysis, cost-effectiveness planes prove to be a valuable tool in the interpretation of the results in an economic equivalence or non-inferiority trial [45]. We consequently will conduct a CUA due to the expected non-inferiorly health outcomes between IA and SCA. Health outcomes (QALYs) between IA and SCA will be compared with incremental costs of intervention between the arms. To assess QALYs gained in each patient group, the EQ-5D-5L instrument will be used on each patient (or representative if the patient is not in a condition of responding) under investigation of this study at screening, the 28th day, and 90th day after randomization. All primary and secondary empirical outcomes will be compared against existing literature and systematic reviews [27, 46, 47] and other trial-based studies. If possible, a meta-analysis will be carried out. The different in costs of interventions in IA and SCA and change in health outcomes (QALYs gained) will be plotted in cost-effectiveness plane for interpreting the results of this non-inferiority trial [45].

iii) Decision-tree analysis

Using data on health outcome (QALYs) and economic outcome (Cost of intervention) and probability of correct diagnosis (including false positives and false negatives) by both procedure arms (IA and SCA) will be used for conducting probabilistic analyses based on a decision-tree using TreeAge Pros (TreeAge Company, Inc) and STATA in a probabilistic CEA. Here, patients are randomly drawn from the IA and SCA treatment arm datasets in a MonteCarlo procedure, until convergence to stable estimates. The patients may face adverse effects of treatment with antibiotics in both arms and consequently worse health status. Patients correctly treated may face different outcomes in terms of cure and health status change and related resources. All resource use, including those of complications will be related to specific costs of NHS services. Following the TreeAge pathways using transition probability distributions between health states, based on the in-trial findings and literature, costs and health utility (health status) we shall be able to estimate expected societal and health care costs and expected utility of the patients (expressed in QALYs placed in IA and SCA).

4) Cost-benefit analysis

Net cost of benefits (all accumulated benefits in monetary term) will be compared with costs of intervention. In this case, potentially avoided cost, for instance due to less use of antibiotics, less hospitalization days, less productivity loss of patients and caregivers and any such loss, in IA in comparison with SCA would constitute the benefits of the intervention. These benefits will be compared with the intervention costs (incremental as described under point 2). If the benefits are higher, the intervention would be useful for implementation [44].

19 Data Management

The source data for PRONTO trial will be from a variety of sources. Data will be collected using an electronic system with paper CRF back up. There will also be data collected from participants' medical notes and patient reported questionnaires. Source data from the BRAHMS PCT direct reader will be recorded, printed and stored electronically in individual

patient folders within the Trial Master File (TMF). Derived data from this source will be entered into the trial database.

Training for completion of study CRFs will be provided to the appropriate trial staff prior to trial commencement at site initiation.

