risk groups. The key outcome measures will be whether IV antibiotics are started, and death within 28 days. An analysis will be done to understand how well clinicians follow the recommendations, ease of use of the additional test in a busy ED, and its cost effectiveness. A sample of patients interviewed at 90 days follow up will assess experiences of care.

4 Background

Sepsis is defined as life-threatening organ dysfunction caused by a dysregulated host response to infection [1] and is a medical emergency requiring prompt antimicrobial therapy and physiological support. The identification, assessment and management of sepsis is challenging because of its many non-specific symptoms and signs, which can be caused by both infectious and non-infectious diseases. In line with international recommendations, National Institute for Health and Care Excellence (NICE) sepsis guidelines suggest the administration of intravenous antibiotics within an hour to patients displaying features considered to be high risk for ICU admission and death [2]. However, up to 50% of patients initially managed as sepsis in the Emergency department (ED) do not have a final diagnosis of sepsis [3, 4]. The current approach leads to overuse of antibiotics with the associated risk of antimicrobial resistance (AMR). For example, since introduction of the National Commissioning for Quality and Innovation (CQUIN) for sepsis in 2015, intravenous broad spectrum antibiotic use in Emergency Departments has increased by 83% over 3 years [5].

Use of antibiotics brings its own problems including antibiotic-related adverse drug reactions (e.g. *C. difficile* infection) [6], extended hospital stays, and generation of antimicrobial resistance with increased long term adverse consequences to health care. There is some evidence that unnecessary use of broad spectrum antibiotics increases the risk of developing sepsis within 90 days of a previous hospital stay [7]. The O'Neill report on antimicrobial resistance suggests that there are about 1 million deaths a year as a result of AMR and this is likely to rise to an estimated 10 million by 2050 [6]. One of the key recommendations was to promote new, rapid diagnostics to improve accuracy of early diagnosis and cut unnecessary use of antibiotics.

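### The cost-of-illness formula (sepsis incidence times unit cost) yields an aggregate for sepsis cases, not the promised cost per randomised patient in each arm

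*Protocol*

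**What the plan says.** Section 18.2 lists four economic analyses, all to follow the intention-to-treat approach of the main trial. The first is "Cost of illness per patient from sepsis in intervention arm (IA: PCT + NEWS2) and standard care arm", from the NHS and household perspectives.

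Section 18.2.1, part 1, gives the method. Its opening sentence labels the result as both a total and a cost per patient, and forms it "by multiplying the total incidences of sepsis with the unit cost of caring for a patient throughout an episode", with the episode running to 28 days after discharge. Screening is then added: "In addition, the total cost of screening will be included, again both from health service and household perspective". The mean cost comes from a costing sample: "30 patients of each type (general ward and ICU), of 10 hospitals will be included to calculate the mean costs of illness", 600 patients in all. The paragraph ends: "By multiplying mean cost with incidence rates, the total costs will be estimated".

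The trial enrols patients with suspected sepsis (Section 8.1). Section 4 reports that "up to 50% of patients initially managed as sepsis in the Emergency department (ED) do not have a final diagnosis of sepsis".

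**The concern.** Three things do not fit together.

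- **The quantity.** The method sentence calls its result both total and per patient, but a count of cases times a cost per case can only be a total.
- **The population.** The trial randomises suspected cases, and the formula counts sepsis cases. A randomised patient who is not counted as sepsis contributes a screening cost and no cost of care. That is at odds with intention to treat. It also drops the care costs of patients who may not need antibiotics, a group the lay summary (Section 3.1) names as a target of the intervention.
- **The source.** The formula needs an incidence of sepsis, and the protocol names no source for it. An individually randomised trial in EDs has no population denominator of its own, and Table 1 lists no final diagnosis of sepsis.

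At stake is whether the first economic output can be read as what Section 18.2 says it is.

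**Working it through.** **Inputs from the protocol:** 7676 patients randomised 1:1, so 7676 / 2 = 3838 per arm; up to 50% of patients initially managed as sepsis without a final diagnosis of sepsis (Section 4); costing sample of 600 (Section 18.2.1).

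**Assumed inputs, because the protocol gives no costs:** cost of a sepsis episode U = 1.0; care of a suspected case without sepsis v = 0.3 to 1.0 of U; screening 0.05 of U per patient; share counted as sepsis p = 0.50 or 0.75.

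**1. The plan's own figure.** 30 × 2 × 10 = 600, as stated.

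**2. What the formula returns.** With a count of cases, 3838 × 0.50 × 1.0 = 1919 U per arm, which is an aggregate. The cost per sepsis patient is U itself, before any multiplication. The product becomes a figure per randomised patient only if incidence is read as a proportion: p × U = 0.50 U. It then covers sepsis cases only.

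**3. What that reading omits.** With screening added, the formula gives p × U + 0.05. The mean over all randomised patients is p × U + (1 − p) × v + 0.05. The omitted part is (1 − p) × v.

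| p | v | Formula with screening | Mean over all randomised | Omitted share |
|---|---|---|---|---|
| 0.50 | 0.3 | 0.55 | 0.70 | 0.15 / 0.70 = 21% |
| 0.50 | 1.0 | 0.55 | 1.05 | 0.50 / 1.05 = 48% |
| 0.75 | 0.3 | 0.80 | 0.875 | 0.075 / 0.875 = 9% |
| 0.75 | 1.0 | 0.80 | 1.05 | 0.25 / 1.05 = 24% |

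Because Section 4 gives an upper limit for patients without sepsis, p = 0.50 is the extreme case on that figure.

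**4. Whether the costing sample fills the gap.** The only per-patient mean in the paragraph comes from 30 × 10 = 300 general-ward and 300 ICU patients. Both groups are admitted patients, so people sent home from the ED are not represented. The two groups are equal in size by design, so a plain average need not match the case mix. The sampling sentence does not mention arms. This mean is therefore not a mean by arm over the randomised population.

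**5. Whether sepsis is shorthand for every randomised patient.** Other text speaks against it. Part 3 of Section 18.2.1 separates a cost per screened patient from a cost per treated sepsis patient, and its decision tree allows for false positives and false negatives.

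**The case against.** The strongest defence is that this is one stray phrase. The last sentence of the paragraph correctly calls mean cost times incidence a total, and the mean cost could serve as the per-patient figure. A cost of illness of sepsis also excludes other illness by definition, and screening of all patients is included. Part of this stands: the closing sentence is right, and suspected cases without sepsis are not wholly absent. But item 1 promises a cost by arm under intention to treat, and the only mean on offer comes from ward and ICU patients chosen by type (step 4). Deleting the phrase alone would leave item 1 without a method.

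Two stronger readings are tempting, and the protocol supports neither.

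- **A biased difference between arms.** PCT is measured only in the open-label intervention arm, so a reader might infer that sepsis would be diagnosed less often there and that costs would fall through labelling alone. If 50% were labelled sepsis in one arm and 45% in the other with identical spending, the totals would differ by 1 − 0.45 / 0.50 = 10%; at 40% the figure would be 20%. These percentages only restate the assumed shift. The protocol nowhere says that incidence will be counted by arm. Its other comparisons between arms use inputs consumed, antibiotic doses avoided and patients drawn from the arm datasets. A common incidence multiplier would leave the ratio between arms unchanged.
- **A total that is half the true one.** This needs a mean cost taken over all suspected cases, exactly 50% of them with sepsis, and no screening cost. The protocol takes the mean from ward and ICU patients, gives 50% as an upper limit, and adds screening.

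**Conclusion.** The concern holds in limited form. As written, part 1 of Section 18.2.1 does not produce the cost per patient by arm that Section 18.2 promises. This follows from the text and needs no assumption about costs. The omission of care costs for randomised patients not counted as sepsis follows from the formula, provided that sepsis does not mean every suspected case. Its size is illustrative: 21% to 48% of mean cost at a 50% sepsis share and 9% to 24% at 75%, on the assumed costs above.

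The missing source for incidence is a weakness of the stated formula. A later plan could name one, but the product would still be an aggregate. Distortion between arms through labelling is a hypothetical risk. The point affects one secondary economic item and touches neither co-primary outcome nor the sample size. No stated decision rule depends on it. It should be corrected because the correction is cheap.

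**What to change.** In Section 18.2.1, part 1:

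1. Define cost of illness per patient as the mean, by arm, over all randomised patients of each patient's resource use times unit cost. Include patients discharged from the ED and those without sepsis.
2. Use the 600-patient costing sample to supply unit costs, weighted to the actual case mix where needed, and not as the population over which the mean is taken.
3. Delete the per-patient wording from the sentence on totals.
4. If a population total is wanted, report it separately: multiply each arm's mean by one common external number of ED attendances with suspected sepsis.

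Resource use is already collected on trial patients (Sections 11.1 and 11.2), so no new outcome is needed. The cost is the rewording and some extra analysis to link the costing sample to all randomised patients.
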